through the study's private group pages. If participants wish to have private study interactions with study staff they can do so at any time. Three-month follow-up assessments will be emailed to participants upon completion of treatment.

Informed consent, baseline and 3, 6, and 12 month assessments will be delivered using the online survey program Qualtrics, which is HIPAA-compliant, has been used often in medical research, and is being used successfully by [name] for her current Facebook intervention study. Verification of non-smoking status will be conducted for all participants reporting no smoking in the past 7 days at the post-test assessment using mailed saliva cotinine test kits and verified online as described in the **Measures** section. Participants will receive their choice of Amazon or Best Buy gift cards in the amount of \$20 for each 20-30 minute online survey, and a bonus \$20 for completing all assessments, for a total of \$100 possible compensation for participation. Amazon and Best Buy were chosen as retail outlets given their overwhelming popularity among a large choice of retailers given in [name] previous studies with young adult smokers.^{4, 111} Assessments will not be considered complete until staff receives verification of abstinence.

Measures.

Primary outcome (tobacco):

- **Biochemically-verified 7-day point prevalence abstinence from all tobacco products** will be assessed at 3, 6, and 12 months. Participants reporting no smoking in the past 7 days will be coded as abstinent from cigarettes. Those reporting 7-day abstinence will be mailed a saliva cotinine test kit, and record two pictures: one giving a saliva sample, and another of the test result. Participants with a salivary cotinine level <11 ng/ml, indicating nonsmoking,¹⁶³ will be considered confirmed nonsmokers. Biochemical verification is recommended in randomized trials with sample sizes under 500,¹⁶⁴ saliva cotinine test kits have been successfully mailed to participants in previous studies,¹⁶⁵ and [name] is using this method successfully in her K23 Facebook smoking cessation RCT with young adults (to date, 50% reporting 7-day abstinence have successfully completed biochemical verification). If participants indicate use of an electronic nicotine delivery-system to aid in smoking cessation, saliva cotinine and reported ENDS use will be recorded and reported separately from biochemically verified abstinence.

Secondary outcomes (tobacco):

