Feasibility analyses will examine four areas: **(1) Recruitment Efforts:** We will evaluate (a) length of time to recruit N=160 participants to enroll in the pilot trial, and (b) demographic, smoking, and drinking characteristics of those eligible and who enroll; **(2) Usability:** We will calculate mean responses to Likert scale items of the usability measure and any sections with lower than median values will indicate changes should be made before future investigations take place. **(3) Implementation of biochemical verification of tobacco abstinence:** We will determine the proportion of participants in each condition reporting 7-day point prevalence abstinence at 3-month follow-up that completes a saliva cotinine test and the rate of discordance between saliva cotinine results and self-report. **(4) Attrition:** We will track the number and proportion of participants that completes each follow-up assessments and compare these numbers to previous Internet cessation trials (attrition as high as 75%^{52, 53, 199-201}).

Analyses for Specific Aim 2: Preliminary efficacy.

Descriptive statistics will summarize sample characteristics and the extent of intervention delivery in each group. We will examine treatment condition and baseline descriptive characteristics as predictors of

attrition at trial end (month 3) and propose to control for predictors of attrition as covariates in model testing. Missing data will be minimized through online assessment. When subjects do not complete online assessments, they will be re-contacted through Facebook or email to obtain missing information. For each test related to smoking, two sets of outcome analyses will be conducted - one with all participants who are maintained in the study, and another based only on biochemically verified smoking abstinence rates to allow for direct comparison of findings with the research literature.

Primary outcome: To test for the effects of treatment condition on smoking abstinence at 3- through 12-months, we will estimate and test a mixed-effects logistic regression model. Abstinence status will be examined as 7-day point prevalence. The independent variables are TSP versus TSP+ALC plus variables that are related to abstinence such as cigarettes per day, differ by condition at baseline or predict attrition. We will use multiple imputation procedures to impute missing data.

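### Self-report precedes a mailed cotinine kit, with no sample date or repeat smoking question, so the discordance rate cannot separate false reporting from relapse after the survey

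*Combined protocol and SAP*

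**What the plan says.** **Order of events.** C.8 (Procedures) states: "Informed consent, baseline and 3, 6, and 12 month assessments will be delivered using the online survey program Qualtrics". Under Measures, Primary outcome (tobacco), "Participants reporting no smoking in the past 7 days will be coded as abstinent from cigarettes". The next step is "Those reporting 7-day abstinence will be mailed a saliva cotinine test kit". The participant photographs the sampling and the test result. The threshold is given as "Participants with a salivary cotinine level <11 ng/ml, indicating nonsmoking". Procedures adds that an assessment stays open until staff have the verification, and gives no deadline.

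**Use of the result.** Verified abstinence is the primary outcome. C.9, feasibility item (3), also plans to report kit completion among reporters at the 3-month follow-up and "the rate of discordance between saliva cotinine results and self-report".

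**Timing of verification.** Measures says the verified outcome "will be assessed at 3, 6, and 12 months". Procedures says: "Verification of non-smoking status will be conducted for all participants reporting no smoking in the past 7 days at the post-test assessment". That sentence goes on to refer the reader to Measures. C.9 models abstinence from 3 through 12 months.

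The documents give no mailing time, no recorded sample date, no limit on the days from survey to sample, and no repeat of the smoking question at sampling.

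**The concern.** The self-report covers the seven days before the survey. The cotinine result reflects a period before the sample, and the sample cannot be taken until a kit has been mailed, received and used. Behaviour can change in between, in either direction:

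- A participant who was truthfully abstinent at the survey and then relapses is coded unverified and counted as discordant.
- A participant who misreported and then stops before sampling can be coded verified and counted as concordant.

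The discordance rate is meant to show whether self-report can be trusted and whether mailed verification works. False reporting and later relapse call for different responses when the larger trial is designed, and the data as planned cannot tell them apart.

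**Working it through.** **1. The plan's own figure.** C.8 gives N = 160 and 30% attrition: 160 × (1 − 0.30) = 112, and 112 / 2 = 56 per group. This reproduces the stated figures, and nothing below changes them.

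**2. Can the windows separate?** Let the sample be taken L days after the survey, and let cotinine reflect the W days before the sample (W up to 7). Overlap with the self-reported week is max(0, W − L) days. Neither L nor W is in the documents; the values below are assumptions.

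| W (days) | L = 1 | L = 3 | L = 5 | L = 7 | L = 14 |
|---|---|---|---|---|---|
| 3 | 2 | 0 | 0 | 0 | 0 |
| 5 | 4 | 2 | 0 | 0 | 0 |
| 7 | 6 | 4 | 2 | 0 | 0 |

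With a short lag the windows can partly overlap. Once the lag reaches the look-back they do not overlap at all.

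**3. Discordance from timing alone.** Suppose every report is truthful and a share h relapses per week. Discordance is then 1 − (1 − h)^(L/7). The values of h are assumptions.

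| h per week | L = 7 | L = 14 |
|---|---|---|
| 2% | 2.0% | 4.0% |
| 5% | 5.0% | 9.8% |
| 10% | 10.0% | 19.0% |

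**4. How many tests carry the rate?** Inputs: 112 completers (C.8); reported abstinence of 21% at 6 months and 18% at 12 months in the feasibility trial (preliminary work, before C.3); 50% of reporters completing verification so far in the ongoing trial (C.8, Measures). The documents give no reported-abstinence rate for month 3, so the later rates stand in for it.

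- 112 × 0.18 × 0.50 = 10.1 tests; one case is 100 / 10.08 = 9.9 points.
- 112 × 0.21 × 0.50 = 11.8 tests; one case is 100 / 11.76 = 8.5 points.

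Split by condition there would be about 5 to 6 tests per arm (10.08 / 2 = 5.0; 11.76 / 2 = 5.9). With 11.76 tests, the 2% and 19% ends of the range in step 3 give 0.24 and 2.23 timing-only discordant cases.

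**5. Primary outcome.** The ongoing trial found 7.1% verified at 3 months among completed TSP cases. Applied here, 0.071 × 56 = 3.98 verified per arm. That trial uses the same mailed method, so the count is already net of any such loss. If a share r of true quitters relapses before sampling, the count without that loss is 3.98 / (1 − r):

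- r = 10%: 4.42, a loss of 0.44 person per arm.
- r = 20%: 4.97, a loss of 0.99 person per arm.

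One person is 1 / 56 = 1.8 points. The 10% to 20% range is an assumption.

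**6. Reported against verified abstinence in the feasibility trial.** If the 50% completion rate had applied there (assumption), non-completion alone would give 0.21 × 0.50 = 10.5% and 0.18 × 0.50 = 9.0%, against 9% verified at both visits.

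**The case against.** The strongest defence has four parts.

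- **The lag is unknown.** It may be a few days, in which case the windows could partly overlap. This stands: a mismatch is possible and its extent unknown, so it would be too strong to say that the two measures always describe different weeks.
- **The comparison of arms is little affected.** The procedure is the same in both arms, nothing in the plan suggests that the error would differ between them, and C.8 says that N was not set by effect size or hypothesis testing. C.9 also plans a second smoking analysis with everyone kept in the study, which on a natural reading uses self-report and is not affected by sample timing. This stands for the primary outcome and does not help the discordance rate.
- **Kit completion is already reported separately from discordance** in feasibility item (3). This is true, so unreturned kits need not be confused with discordance. It does not separate relapse from misreporting among those who test.
- **A strict limit on the interval could do harm.** With 10 to 12 tests, coding late samples as unverified could remove as many events as it rescues. This stands and shapes the fix.

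Two stronger readings are tempting, and the documents do not support them:

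- A reader might infer that verification is confined to the post-test visit, so that about 10 verified quitters (0.09 × 112 = 10.1) would be lost at each of months 6 and 12. The Procedures sentence does not say only, does not define post-test, and defers to Measures, which names all three visits. The wording needs reconciling; it is not a restriction.
- A reader might take the fall from 21% to 9%, or from 18% to 9%, as a sign of relapse while the kit is in transit. Step 6 shows that non-completion alone could account for nearly all of it.

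Setting feasibility item (3) at 3 months is a reasonable choice. Extending it to later visits would be a preference.

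**Conclusion.** The point holds as a cheap improvement in measurement. As written, the plan cannot separate false reporting from relapse after the survey, and a late quit can pass as verification of an earlier report. The discordance rate bears most of this: about 10 to 12 tests per timepoint, with one post-survey relapse worth about 8.5 to 10 points. That size rests on carrying the feasibility trial's reporting rates and the ongoing trial's kit completion over to this study. The effect on the primary outcome is likely small, under about one person per arm if 10% to 20% relapse before sampling, with no stated reason for it to differ by arm. The actual lag, cotinine look-back and relapse rate are not in the documents. No sample-size figure changes.

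**What to change.** At the existing photo upload:

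1. Record the date of the sample.
2. Repeat the 7-day tobacco question, ideally answered before the test result is read.

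In C.9, feasibility item (3), calculate discordance against the answer given with the sample. Report relapse between survey and sample as a separate figure, and summarise the survey-to-sample interval. Use any limit on that interval only in a sensitivity analysis.

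As a wording correction, reconcile the post-test reference in C.8 Procedures with the 3, 6 and 12 months in Measures.

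The cost is two extra items for participants who self-test, plus short edits to C.8 and C.9.

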In a 3-year controlled trial, we are randomizing 480 young adult participants to either TSP or referral to the National Cancer Institute Smokefree.gov website (control). In 34 weeks, we have randomized 309 young adult smokers, consistent with the proposed timeline, 19% were ready to quit smoking in the next 30 days, and the TSP group has 19 groups actively running or completed. Among TSP participants in groups that have completed the 3-month intervention (n=66), 73% commented at least once to their Facebook group. At 3 month follow-up (treatment end), follow-up rate is 71%, biochemically-verified 7-day point prevalence abstinence among completed cases is 7.1% in the TSP group and 0% in the control group. A majority of participants in both groups reported a 24 hour quit attempt during the 3-month intervention period (62% TSP; 60% control). More participants in the TSP group reported intention to quit smoking in the next 30 days (43%) than those in the control group (35%). At baseline 68% of the sample drank alcohol in the past month and 51% of all drinkers reported current HED. Although promising, there is a need to determine whether expanding the intervention to address multiple substance use will yield maximal effectiveness. **This pilot work will directly inform the present study.**

Facebook Recruitment. Drs. [name] and [name]'s research has previously found social media to be an efficient and affordable source of recruitment for young adult smokers. A survey study (N=1987) reported a cost of \$4.28 per valid completed online survey, far more affordable and targeted than other online recruitment methods.¹¹⁰ The TSP feasibility trial, discussed above, reported a cost of \$8.80 per eligible consented young adult smoker into our Facebook intervention.¹¹¹ Gender and ethnicity have differed by online recruitment source in our work (e.g., Craigslist, Facebook, survey sampling), suggesting the utility of combining recruitment methods.¹¹² **Our experience with social media recruitment will inform recruitment in the present study.**

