- **Reduction of cigarette consumption by 50% or more (y/n)** between baseline each follow-up will be calculated from the number of cigarettes smoked in the past 7 days at each time point.
- **Tobacco quit attempt (y/n)**. A *Follow-up Smoking Questionnaire* will assess the presence and number of 24 hr quit attempts since the last assessment, used to calculate presence of at least one quit attempt in the assessment time period. This questionnaire has good internal consistency and construct validity, and is routinely used in smoking treatment research.
- **Readiness to quit tobacco** will be assessed using the *Stages of Change Questionnaire*,¹²⁹ categorizing participants into five stage categories at each timepoint (precontemplation, contemplation, preparation, action, and maintenance), and predictive of quit attempts and cessation.¹⁶⁶
- **Desire to quit, abstinence self-efficacy, perceived difficulty of quitting and abstinence goal** will be assessed with the 4-item *Thoughts About Abstinence Form*,¹⁶⁷ measuring each construct on a scale from 1 ("least") to 10("most"), and categorizing goal as no goal, intermediary goal (e.g., reduced smoking), or total abstinence.

These smoking measures demonstrated significant improvement from Baseline to 12 months in the TSP feasibility trial,⁷ and have demonstrated validity for use with young adult smokers online.^{168, 169}

Secondary outcomes (alcohol):

- **Days of HED.** Past 30 day HED episodes, defined as 4+ drinks in an occasion for women and 5+ drinks for men, consistent with the NIAAA definition¹⁶ will be assessed with the *Timeline Followback* (TLFB). The TLFB has good reliability and validity for tobacco and alcohol and administered online.¹⁷⁰⁻¹⁷³ Past 30 day use is a commonly-used assessment timeframe,¹⁷⁴ and self report measures such as the TLFB can be accurate,¹⁷⁵⁻¹⁷⁷ and are the most common outcome measures for clinical trials.¹⁷⁸
- **Number of drinks per week** assessed by the *TLFB*.
- **Misuse of alcohol in the past year** will be assessed by the *Alcohol Use Disorders Identification Test-C* (AUDIT-C; 3-items; range: 0-12).¹⁷⁹⁻¹⁸¹ Used widely in the literature, cut-off scores of 3 in women and 4 in men have demonstrated good sensitivity and specificity compared to longer clinical interviews.¹⁸²

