- **Alcohol quit attempt (y/n)**. A *Follow-up Drinking Questionnaire* will assess the presence and number of 24 hr quit attempts since the last assessment, used to calculate presence of at least one quit attempt in the assessment time period.

- **Readiness to change alcohol use** will be assessed with a single-item **Readiness Ruler**, developed and validated for use with young adult heavy drinkers participating in brief intervention.^{183, 184} and the alcohol item from the **Staging Health Risk Assessment (S-HRA)**^{185, 186} to compare stage of change across tobacco and alcohol use.
- **Desire to quit HED, abstinence self-efficacy, perceived difficulty of quitting and abstinence goal** will be assessed with an adapted *Thoughts About Abstinence Form* for HED.
- **Thoughts about alcohol** will be assessed the *Thoughts About Abstinence* form, adapted for alcohol.

Secondary outcome (combined days using tobacco or alcohol):

- *TLFB* data will be used to calculate the sum of days using any tobacco or binge drinking in the past month.

Additional measures.

- **Demographics.** Age, gender, ethnicity, parental and personal education, work/school status, military involvement, parental status, and other personal characteristics will be assessed at baseline with a *Demographic Questionnaire* used in our prior research with young adults.¹⁶⁹
- **Smoking History.** The *Smoking History Questionnaire*¹⁵⁸ at baseline will assess age of initiation and years of smoking; prior quit attempts and cessation strategies; other nicotine (e.g., electronic nicotine delivery systems) and tobacco use (e.g., cigars); nicotine dependence using the 6-item *Fagerström Test of Cigarette Dependence (FTCD)*,^{187, 188} and social smoking with 3-items used with young adults.^{189, 190}
- **Alcohol Use history.** We will assess age of first drink and first heavy drinking episode, prior attempts to change HED, and change/cessation strategies.
- **Combined alcohol and tobacco use.** Two items assessing subjective effects of smoking while drinking (estimated overlap and pleasure), previously used with college students,³⁴ will be given at baseline.
- **Drug Use Severity.** The *Drug Abuse Screening Test-10* (DAST; 10 items),¹⁹¹ will assess misuse of drugs in the past year. Used widely in the literature, a cut-off score of 2 has demonstrated good sensitivity and specificity compared to longer clinical interviews.¹⁹²

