Secondary outcomes: For secondary outcomes we will estimate and test mixed effects logistic and multinomial regression models for longitudinal ordinal response data to model secondary outcomes for tobacco use and alcohol use across time (3, 6, 12 months): 1) reduction of cigarettes by 50% or more (y/n), 2) tobacco or alcohol quit attempt (y/n; 2 models), 3) readiness to quit tobacco and alcohol (Precontemplation, Contemplation, Preparation, Action/Maintenance; 2 models); and 4) commitment to abstinence (no goal, intermediary goal, complete abstinence). In parallel, mixed effects linear regression models will model the following continuous outcomes over time: 1) past 30 day HED; 2) average number of drinks per week in the past 30 days, 3) severity of alcohol use (AUDIT-C score); 4) desire to cut down tobacco and alcohol use (1 to 10; 2 models); and 5) sum of days using either tobacco or alcohol in the past 30 days. Independent variables in all models will be treatment condition, abstinence status, and covariates identified as relevant to smoking characteristics in the literature.

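### The quit-attempt question runs back to the previous assessment, so one yes/no outcome covers 3, 3 and 6 months, and the listed model terms include neither visit nor window length

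*Combined protocol and SAP*

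**What the plan says.** Under C.8, Measures, the smoking questionnaire "will assess the presence and number of 24 hr quit attempts since the last assessment", and the answer is "used to calculate presence of at least one quit attempt in the assessment time period". The alcohol item is built the same way: "A *Follow-up Drinking Questionnaire* will assess the presence and number of 24 hr quit attempts since the last assessment", again reduced to yes/no.

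The schedule is in C.8, Procedures: "Informed consent, baseline and 3, 6, and 12 month assessments will be delivered using the online survey program Qualtrics".

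C.9, Secondary outcomes, fits longitudinal mixed-effects models to "secondary outcomes for tobacco use and alcohol use across time (3, 6, 12 months"), and lists "tobacco or alcohol quit attempt (y/n; 2 models") among the outcomes. The regressors are then stated for every secondary model: "Independent variables in all models will be treatment condition, abstinence status, and covariates identified as relevant to smoking characteristics in the literature". Visit, time and window length are not in that list.

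No section says which assessment counts as the last one for a person who skipped a visit. C.9 says only that non-completers will be contacted again.

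**The concern.** Whether someone made at least one attempt depends on how long a period they are asked about. An outcome that covers 3 months at two visits and 6 months at the third is not the same quantity throughout. A rise from month 6 to month 12 could come from the longer window with no change in behaviour, and a model without a visit term averages over the two kinds of window.

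Other behavioural measures in C.8 avoid this by using fixed periods: 7 days for cigarettes smoked, 30 days for heavy drinking episodes, a year for AUDIT-C. The quit-attempt items are an exception. The trial is meant to supply estimates for planning a larger one, so a rate with an unclear time base loses some of its use.

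**Working it through.** **1. The plan's own figure.** The plan gives no expected quit-attempt rate or power for this trial. Its retained sample (C.8, Sample size) reproduces: 160 × (1 − 0.30) = 112, or 56 per arm.

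**2. Window lengths.** From visits at 0, 3, 6 and 12 months:
- All visits completed: 3 − 0 = 3, 6 − 3 = 3, 12 − 6 = 6 months.
- Month 3 missed: 6 − 0 = 6 months at month 6.
- Month 6 missed: 12 − 3 = 9 months at month 12.
- Both missed: 12 − 0 = 12 months at month 12.

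The last three lines assume that the question reaches back to the last completed assessment.

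**3. How many people have a lengthened window.** C.8 expects 30% attrition at each follow-up but not its pattern. If misses were independent between visits, 30% of month-6 attenders would have a 6-month window. Month-12 attenders would split 70% (6 months), 0.30 × 0.70 = 21% (9 months) and 0.30 × 0.30 = 9% (12 months). If people who drop out never return, the share is 0% at both visits.

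**4. What a longer window does to the rate.** Two figures come from the preliminary work that precedes C.3. In the ongoing trial, "A majority of participants in both groups reported a 24 hour quit attempt during the 3-month intervention period (62% TSP; 60% control"); the mid-point is 61%. In the feasibility trial, 67% reported an attempt between baseline and 12 months. The curves joining these are assumptions:
- A, constant rate from 61% at 3 months: P(m) = 1 − 0.39^(m/3).
- B, Weibull curve through 61% at 3 months and 67% at 12: P(m) = 1 − 0.39^((m/3)^0.118), with shape [ln(−ln 0.33) − ln(−ln 0.39)] / ln 4 = 0.118.
- C, constant rate fitted only to 67% at 12 months: P(m) = 1 − 0.33^(m/12).

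| Window | A | B | C |
|---|---|---|---|
| 3 months | 61% | 61% | 24% |
| 6 months | 85% | 64% | 43% |
| 9 months | 94% | 66% | 57% |
| 12 months | 98% | 67% | 67% |

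Going from 3 to 6 months adds about 24 points (A), 3 (B) or 18 (C). Going from 6 to 9 months, which is the effect of a missed month 6, adds about 9 points under A and 2 under B.

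**5. Pooled arm comparison with balanced windows.** Take an assumed odds ratio of 1.5 at every visit and average the rates over visits with no visit term. Under A the control rates are 61%, 61% and 84.8%, mean 68.9%. Multiplying each odds by 1.5 gives 70.1%, 70.1% and 89.3%, mean 76.5%. The pooled odds ratio is (0.765/0.235) / (0.689/0.311) = 1.47. Under B it is 1.50. This is simple averaging, not a fitted mixed model, but it shows the order of size.

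**6. Arm bias at month 6 with no true effect.** Suppose the share of month-6 attenders who missed month 3 differs by 10 points between arms. The spurious difference is 0.10 × 24 = 2.4 points under A and 0.10 × 3 = 0.3 points under B. For scale, with 30% of attenders on the longer window, curve A gives a month-6 rate of 0.70 × 61 + 0.30 × 84.8 = 68.1%. With 56 per arm, the standard error of a difference is √(2 × 0.681 × 0.319 / 56) = 8.8 points.

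**The case against.** Both arms share the schedule, so the 3/3/6 pattern does not bias the randomised comparison at any one visit, and C.8 says that groups will be compared at each timepoint. That stands, and step 5 confirms that the pooled effect hardly moves.

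The C.9 wording about modelling across the three visits may imply that time was to be included. That is plausible, but the explicit list for all models omits it, so it needs stating.

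A reader might infer that the 12-month outcome is driven to its ceiling, or that any missed visit adds 24 points. The documents do not support this. A constant rate from 60% implies 1 − 0.4^4 = 97% at 12 months, against the 67% reported in the feasibility trial. That is another trial and its recall item is not described, but it is the only long-window figure available. The 24 points are also the top of the range, and apply only to a missed month 3.

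A reader might also infer that the arm with poorer attendance will collect more positive answers. That needs people who miss a visit and come back, and unequal numbers of them by arm. Nothing in the plan shows either. Both arms use the same platform, session schedule and incentive, and non-completers are contacted again.

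Finally, C.8 describes the smoking questionnaire as established and routinely used, and its present wording covers all 12 months for complete attenders. That is a fair reason to keep it, provided the window is recorded.

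**Conclusion.** The point holds as a cheap improvement to two secondary outcomes in a pilot. On the stated schedule the window is 3, 3 and 6 months, and the listed model terms do not account for it. Quit-attempt rates therefore cannot be compared across visits, and the pooled estimate mixes windows.

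Doubling the window from 3 to 6 months raises the rate by about 3 to 24 points, depending on the assumed curve. The treatment comparison is little affected when windows are balanced. The 0.3 to 2.4 points of bias in step 6 are conditional on an assumed 10-point imbalance, and even the upper figure is only about a quarter of the standard error (2.4 / 8.8). All these figures use tobacco rates from earlier studies of the intervention. The documents give no alcohol quit-attempt rate, so the size for alcohol is unknown, although the structure is identical.

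A visit term alone does not settle the matter: it absorbs the scheduled 3/3/6 difference, but not windows lengthened by missed visits.

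**What to change.** 1. Add visit (3, 6, 12 months) as a categorical factor in both quit-attempt models in C.9. This costs two parameters per model and has no real downside.
2. For missed visits, choose one of two routes and state it for both substances:
   - Ask about a fixed period, such as the past 3 months, at every follow-up. This is a survey wording change. Attempts in months 7 to 9 are then not captured at month 12, and the existing questionnaire's wording is altered.
   - Keep the wording, define the last assessment as the last one completed, record each person's actual window length and include it in the model. Its coefficient should be estimated, because forcing proportionality to time would impose the constant rate that the 67% figure contradicts. The cost is one derived variable. Window length is also settled after randomisation, so the fixed period is the cleaner route.
3. Report quit-attempt rates by visit with the window length stated beside each.
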